### 4.3 Secondary Objectives (if applicable)

To determine the need for hospitalization for symptomatic anemia or acute gastrointestinal bleed

To determine the need for additional endoscopic interventions

To determine the rate of clinically significant side effects associated with TXA therapy leading to drug withdrawal

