## 5 - Study Design

### 5.1 General Design Description

In the RCT portion of the study, we will enroll approximately 50 patients with diagnosed intestinal AEs through VCE and/or endoscopy who experience symptomatic anemia despite standard therapy including endoscopic ablation and iron supplementation. Subjects will be randomized to either the TXA treatment group versus the placebo treatment group for 3 months. Patients will have initial complete blood counts (CBC) measured as a baseline then subsequent CBCs measured at 1, 2 and 3 months. Patients will be monitored for drug side effects, symptoms related to anemia, the need for blood transfusions and hospitalizations related to GI bleeding/anemia.

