#### 5.2.2 Secondary and Exploratory Outcome Variables (if applicable)

Secondary outcome variables include number of hospitalizations, endoscopic interventions (EGD, Colonoscopy, enteroscopy, video capsule endoscopy) and experienced side effects.

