#### 6.1.2 Method of Assignment/Randomization (if applicable)

Allocation concealment will be used to make sure the individual enrolling the trial subjects into the study has no bias towards group assignment. A statistician not directly involved in the analysis of the study will use simple randomization to create the two arms of the study (TXA vs placebo). Randomization will be carried out by using an online random number generating software, excluding the number zero. If an even number is generated, the patient will be placed in the TXA treatment arm, and if an odd number is generated the patient will be placed in the control (placebo) arm. This process will be repeated until there are 25 patients in each group.

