**6.3.4 On Study Visits**

Research study participants will meet for a screening and consent visit. At this time, inclusion/exclusion criteria will be review and if meet then they will be consented for the study. Following, demographic information will be collected, and baseline lab work will be done prior to the start of the interventional portion of the study.

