### **6.4.2 Planned Analyses**

We will characterize subjects with regard to baseline and follow up hemoglobin/hematocrit (H/H) and other endpoints previously described. We will summarize demographics and other predictors of clinical status. Continuous variables will be summarized by mean, standard deviation and range as appropriate. The primary analysis will compare the absolute and percent change in hemoglobin with adjustment for baseline in linear regression models. Using multivariable logistic regression models adjusting for baseline hemoglobin, we will assess if the odds of achieving a clinically relevant improvement in hemoglobin differs by treatment assignment. The secondary outcomes will be analyzed similarly using linear regression models adjusting for baseline values.

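### Linear regression adjusted for an undefined baseline is the wrong tool for the yes/no side-effect outcome: with 25 per arm its interval fails when events are rare and unequal, and has no width when there are none

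*Combined protocol and SAP*

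**What the plan says.** All references are to the combined protocol and SAP. Section 6.4.2 (Planned Analyses) ends with one rule for the whole secondary family: "The secondary outcomes will be analyzed similarly using linear regression models adjusting for baseline values".

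Section 5.2.2 defines that family: "Secondary outcome variables include number of hospitalizations, endoscopic interventions (EGD, Colonoscopy, enteroscopy, video capsule endoscopy) and experienced side effects". Section 4.3 is more specific about the safety part: "To determine the rate of clinically significant side effects associated with TXA therapy leading to drug withdrawal". Two of the outcomes are therefore counts over three months, and the side-effect objective is a proportion of patients.

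The only model for a binary outcome in 6.4.2 is reserved for hemoglobin response: "Using multivariable logistic regression models adjusting for baseline hemoglobin, we will assess if the odds of achieving a clinically relevant improvement". No count, exact or binary method is named for any secondary outcome.

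On baseline data, section 5.1 says "Patients will have initial complete blood counts (CBC) measured as a baseline then subsequent CBCs measured at 1, 2 and 3 months" and section 6.3.4 says "demographic information will be collected, and baseline lab work will be done prior to the start of the interventional portion of the study". Section 6.4.2 also opens with a looser statement: "We will characterize subjects with regard to baseline and follow up hemoglobin/hematocrit (H/H) and other endpoints previously described". No section gives a look-back window or a source for earlier hospitalizations or procedures.

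**The concern.** Two things do not fit. First, the baseline term. A side effect that leads to stopping the study drug cannot exist before the drug is started, so it has no baseline value. For hospitalizations and endoscopic procedures a baseline is conceivable, but the plan does not say what it is, so the analyst would have to choose it.

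Second, the interval. Ordinary linear regression estimates one residual variance from the data. With a rare yes/no outcome in a small trial that estimate is often very small, and it is exactly zero when nobody has an event. The report would then show a difference of zero with no uncertainty. This matters most for safety. Section 3.3.1 singles out thromboembolic events as the gravest risk, and a trial of 50 patients cannot rule out a modest excess. The output should show that plainly.

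**Working it through.** The plan states no rate, power or precision for any secondary outcome, so there is no figure of its own to reproduce. All event rates and means below are my assumptions, shown over a range.

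**Inputs.** Arm size is 25, from section 6.1.2: "This process will be repeated until there are 25 patients in each group". The interval is taken as two-sided 95%. Rates of 1% to 10% are used for rare side effects. As context, the background and section 3.3.1 quote an absolute thromboembolic risk below 1% and below 2% respectively. Rates of 20% and 30% stand for common side effects.

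**Interval from the linear model (arm only).** With observed proportions p1 and p2:

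- s² = [25·p1(1−p1) + 25·p2(1−p2)] / 48
- interval = (p1 − p2) ± t × √(s² × 2/25), with t = 2.011 on 48 degrees of freedom

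**Two observed results.**

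- 1/25 v 0/25: s² = 25 × 0.04 × 0.96 / 48 = 0.02. SE = √(0.02 × 0.08) = 0.04. Half-width = 2.011 × 0.04 = 0.080. The interval is −4.0 to +12.0 points. The Newcombe (Wilson-based) interval is −9.7 to +19.5 points.
- 0/25 v 0/25: s² = 0, so the interval runs from 0 to 0. The Newcombe interval is −13.3 to +13.3 points. Adding baseline hemoglobin to the linear model changes nothing here, because an outcome that is zero for everyone leaves no residual.

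**Coverage.** I summed binomial probabilities over all 26 × 26 possible results and counted those whose interval contains the true difference. The chance of zero width through no events is (1−p1)^25 × (1−p2)^25. At 2% v 1% this is 0.6035 × 0.7778 = 0.469.

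| True rates | Coverage of linear 95% interval | Chance of no events in either arm |
|---|---|---|
| 8% v 0% | 87.3% | 12.4% |
| 8% v 2% | 86.8% | 7.5% |
| 4% v 2% | 77.6% | 21.7% |
| 2% v 1% | 53.0% | 46.9% |
| 10% v 5% | 91.6% | 2.0% |
| 2% v 2% | 99.8% | 36.4% |
| 5% v 5% | 98.0% | 7.7% |
| 10% v 10% | 95.1% | 0.5% |
| 20% v 10% | 95.1% | under 0.1% |
| 30% v 10% | 95.2% | under 0.1% |

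At 2% v 1% almost all the shortfall (100 − 53.0 = 47.0 points) comes from the no-event trials (46.9 points). The high coverage at 2% v 2% is partly an artefact: in 36.4% of trials the interval is a single point at zero, which counts as correct only because the true difference is exactly zero.

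**Same check for the Newcombe interval.** Coverage is 100% at 2% v 1% (linear 53%), 99.9% at 5% v 1% (linear 77.6%), 99.9% at 5% v 2% (linear 82.5%) and 97.9% at 10% v 5% (linear 91.6%). It is conservative for rare events, but it does not collapse.

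**Counts.** I simulated 40,000 trials per setting, with linear regression adjusted for baseline hemoglobin and counts that were Poisson or overdispersed (gamma shape 1 or 0.5). Coverage of the 95% interval for the difference in means was:

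- equal means of 0.1, 0.3 or 1: about 95% to 96%
- 0.29 v 1: 92% to 95%
- 0.1 v 0.3: 92% to 94%
- 0.02 v 0.1: 89% to 91%

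For counts, then, the linear interval is close to nominal unless events are very sparse and unequal.

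**The case against.** The best defense is that linear regression is a legitimate way to estimate a difference in means or risks in a randomized trial, and that much of what might be said against it here goes too far. Several stronger readings are tempting and do not hold.

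- *The model cannot be fitted.* It can. Baseline hemoglobin is collected and is the adjuster named in the sentence before. The linear model gives no usable interval only when there are no events.
- *The baseline values are never collected.* The documents do not say so. They leave the values undefined, and the opening sentence of 6.4.2 mentions baseline for other endpoints.
- *The intervals are wrong for all secondary outcomes.* They are not. Counts with means of about 0.3 to 1 are near nominal, and so are common side effects. Section 6.2.2 lists nausea and diarrhea among the side effects, so not every side-effect comparison concerns rare events.
- *Linear regression wastes power on counts.* This has not been shown at equal type I error. With assumed means of 1 v 0.35 and gamma shape 1 to 2, linear regression with a prior-period count has 63% to 70% power and rejects a true null 5.1% of the time. A log-link model with the same covariate and a simple robust standard error has 70% to 75% power but rejects a true null 5.5% to 7.5% of the time. The mean of 1 is also the plan's transfusion figure; no rate is given for hospitalizations or procedures.
- *Transfusion gets the linear model by default.* Section 5.2.1 lists transfusion as a primary outcome, and 6.4.2 names no model for it. That is a separate gap.

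All of this limits the point to rare side effects and to the undefined baseline. It does not answer either one: a side effect that stops the drug still has no baseline, and a zero-width safety interval is still misleading.

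**Conclusion.** The point stands in a limited form. Applied as written to yes/no side effects, the rule in 6.4.2 asks for a baseline that cannot exist and gives unreliable error bars when events are rare and differ between arms. Nominal 95% coverage falls to about 87%, 78% and 53% at the assumed rates of 8% v 0% or 2%, 4% v 2%, and 2% v 1%. The interval has no width at all in 47% of trials at 2% v 1%. These figures rest on 25 per arm, complete data, an arm-only model and event rates that the documents do not give.

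For hospitalizations and endoscopic procedures, the defect is that the baseline adjuster is not named. The linear interval itself is acceptable over a plausible range of means, and moving to a count model is a choice, not a correction. The primary hemoglobin analysis is unaffected.

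**What to change.** In section 6.4.2:

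1. Take side effects out of the linear-regression sentence. Report n (%) per arm, a score-type (for example Newcombe) or exact 95% interval for the risk difference, and Fisher's exact test, with no baseline covariate. Apply this to side effects that cause the drug to be stopped and to each listed side effect reported as yes/no.
2. For hospitalizations and endoscopic procedures, name the adjuster: either baseline hemoglobin, which is already collected, or the same count over a stated period before enrolment, taken from the chart.
3. Optionally, use a count model for these two outcomes, with log follow-up time as offset and either small-sample-corrected standard errors or a permutation p-value. The offset would deal with unequal follow-up. The effect would then be a rate ratio, not a mean difference, and no power gain should be claimed for it.

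Item 1 costs only SAP wording, plus wider and somewhat conservative intervals for rare events. Item 2 costs wording alone if baseline hemoglobin is chosen. If prior counts are chosen, it also needs a short chart review for each patient, with the look-back period fixed before enrolment.

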### **6.4.3 Handling of Missing Data**

Every effort will be made to secure data and account for all data points. If missing data was to occur, it would be noted during the statistical analysis and clearly outlined in the discussion portion of future manuscripts.

## 7 - Trial Administration

### 7.1 Ethical Considerations: Informed Consent/Accent and HIPAA Authorization

Please find the informed consent statement and HIPAA Authorization attached.

### 7.2 Subject Confidentiality

Every precaution will be taken to allow for data confidentiality. Only members of the research team will have access to the patient information and subsequent study data. Trial participants will be assigned a unique identification number that will be used in future database reporting. All hard copies of data and patient records will be kept in a secure location within [name] office in a locked cabinet.

### 7.3 Deviations/Unanticipated Problems

We will attempt to minimize missing data; however, we have planned for its occurrence. For subjects lost to follow-up, we will use all of the information available until the end of follow-up. This protocol will continue to follow subjects and perform lab tests even if a subject drops-out from the treatment portion of the study. If a subject decides that he/she does not wish to continue taking the study drug, the subject will stop the investigational treatment, but will still be strongly encouraged to continue to follow-up with the study personnel for all scheduled study follow ups (e.g., lab draws and symptom reporting), so that missing data will be minimized.

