### **6.3.6 Removal of subjects**

- At the time of consent, participants will be informed that their participation in this research study is voluntary and they may discontinue participation without penalty at any time.
- Subjects will be withdrawn from the study by the investigator if they are to have serious adverse reactions to TXA or to protect the subjects from excessive risk due to lack of benefit demonstrated by TXA.
- Data collection prior to participant withdrawal may be retained and used in a manner that is consistent with study design and purpose unless participant expresses that their information to not used in the study

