## **6.4 Statistical Method**

### **6.4.1 Sample Size Considerations**

We based our sample size estimate on assumptions for our primary aim, as this is the most important aim for providing information to support future recommendations with regards to TXA in patients with intestinal AE. A total of 50 subjects will be enrolled with 1:1 randomization to either TXA or placebo. For the primary study endpoint of hemoglobin, we will have 80% power to detect an average increase of 25% from baseline to 3 months between TXA and placebo groups ( $\alpha = 0.05$ ). We expect 75% of patients on TXA to have a 2 gm/dl improvement in overall hemoglobin while only 25% in placebo group see a 2gm/dl improvement. We expect 75% of TXA patients to require zero blood transfusions compared to placebo group requiring 1 blood transfusion on average per patient over 3 months.

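### Partial event counts from early leavers are kept with no allowance for time observed, and no analysis is named for the primary transfusion outcome

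*Combined protocol and SAP*

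**What the plan says.** - **Partial data.** Section 7.3: "For subjects lost to follow-up, we will use all of the information available until the end of follow-up". Section 6.3.6 also allows data gathered before a withdrawal to be kept and used.
- **Follow-up after stopping drug.** Section 7.3 goes on to say that patients who stop study drug remain in follow-up, and it encourages them to attend the scheduled assessments.
- **Withdrawal from the study.** Section 6.3.6: "Subjects will be withdrawn from the study by the investigator if they are to have serious adverse reactions to TXA". The same sentence gives a second reason, lack of benefit.
- **Outcomes.** Section 5.2.1 makes transfusion requirement a primary outcome. Section 5.2.2 lists hospitalizations and endoscopic interventions as secondary.
- **How transfusion is framed.** Section 6.4.1: "We expect 75% of TXA patients to require zero blood transfusions", against "placebo group requiring 1 blood transfusion on average per patient over 3 months".
- **Analysis.** The models for the primary analysis in section 6.4.2 are for hemoglobin. For the rest: "The secondary outcomes will be analyzed similarly using linear regression models adjusting for baseline values". No comparison of transfusion between arms is named. No rate, offset, person-time or censoring appears anywhere.
- **Missing data.** Section 6.4.3 says that missing data will be noted and discussed, and gives no method.

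**The concern.** Transfusions, hospitalizations and endoscopies accumulate with time. A patient seen for one month has a third of the opportunity to have an event that a patient seen for three months has. If the one-month count enters a comparison as though it covered the full window, short follow-up looks like good control of bleeding.

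For the two secondary counts, the stated model has no term that could correct this. For transfusion, the plan offers only a 3-month framing and leaves the analysis open, so nothing prevents a comparison of raw totals or of the raw share with zero. At stake are one of the two primary outcomes and two secondary outcomes, in a trial with 25 patients per arm, where five leavers are 20% of an arm.

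**Working it through.** **The plan's own figures.** There is none for this point: no dropout rate, leaving time or transfusion power is given. The only power statement, "we will have 80% power to detect an average increase of 25% from baseline to 3 months between TXA and placebo groups", concerns hemoglobin. It comes without an SD, so it cannot be reproduced. Read as a 25-point difference in percent change (two-sided), it needs an SD of 25 / ((1.960 + 0.842) × √(2/25)) = 31.5 points. The present point does not depend on it.

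**Inputs from the documents**
- 25 per arm: "A total of 50 subjects will be enrolled with 1:1 randomization to either TXA or placebo".
- Placebo rate λ = 1 per 3 months (section 6.4.1).
- TXA: 75% with none (section 6.4.1). Under a Poisson model this is a mean of −ln(0.75) = 0.288.

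**Assumptions.** Counts are Poisson. A fraction d of an arm leaves after a share t of the 3 months. Leaving is unrelated to bleeding. Counts are compared as totals.

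**Formulas**
- Mean raw count = λ × [1 − d(1 − t)]
- Share with zero = (1 − d)e^(−λ) + d·e^(−λt)

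**No drug effect, λ = 1.** A patient followed for 3 months has zero transfusions with probability e^(−1) = 36.8%. For one who leaves at month 1 it is e^(−1/3) = 71.7%.

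| Leaving (d) | Mean, leaving at month 1 | Zero, month 1 | Mean, leaving at month 2 | Zero, month 2 |
|---|---|---|---|---|
| 0% | 1.000 | 36.8% | 1.000 | 36.8% |
| 10% | 0.933 | 40.3% | 0.967 | 38.2% |
| 20% | 0.867 | 43.8% | 0.933 | 39.7% |
| 30% | 0.800 | 47.2% | 0.900 | 41.2% |
| 40% | 0.733 | 50.7% | 0.867 | 42.6% |

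**Comparing arms, leavers at month 1**
- 20% v 0%: 0.867 / 1 = 0.867, or 13% fewer; 43.8% v 36.8% with none.
- 20% v 10%: 0.867 − 0.933 = −0.07 per patient.
- 30% v 10%: 0.800 / 0.933 = 0.857, about 14% fewer; −0.13 per patient.
- 40% v 10%: 0.733 / 0.933 = 0.786, about 21% fewer; −0.20 per patient.

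The ratio of means does not involve λ. The same percentages therefore apply to hospitalizations and endoscopic interventions, for which the plan gives no rates. The zero share does depend on λ: with 20% leaving it rises by 4.8 points at λ = 0.5 and by 7.6 points at λ = 2.

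**Effect on the test.** In 20,000 simulated trials per setting, raw counts were compared by t test. The nominal 2.5% chance of a false result favouring the arm with more leavers became 7.1% (30% v 10%) and 11.2% (40% v 10%). With overdispersed counts (gamma-distributed patient rates, shape 1) it became 5.4% and 7.6%. Using events per person-time, the mean difference was about zero in every case.

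**Opposite direction.** Take the planned rates (0.288 v 1) with 10% of TXA and 30% of placebo leaving at month 1. The expected raw difference is 0.288 × 0.933 − 0.800 = −0.53, against −0.71 with no leavers. The bias now works against TXA.

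**The case against.** A reader might infer that the plan scores an early leaver as a transfusion success and so tilts the trial towards TXA. The documents do not support that.

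- Section 6.4.2 names no transfusion analysis. Its linear regression sentence covers secondary outcomes, and transfusion is primary. The zero-transfusion figure is an expectation in sections 4.1 and 6.4.1, not a defined endpoint or success. Section 7.3 says that available information is used; it does not say that a partial count is treated as a 3-month total.
- Section 7.3 keeps following patients who stop study drug. Only those lost, or withdrawn from the study under section 6.3.6, have shortened observation.
- Section 6.3.6 has two withdrawal reasons. Reactions could shorten follow-up on TXA. Lack of benefit could shorten it on placebo if TXA works, and such patients are unlikely to be event-free.
- The illustration rests on assumed losses. Section 2.2 reports no side effects in nine treated patients, though that experience is small and uncontrolled. The 7-point gap at 20% v 0% is 25 × 0.070 = 1.7 patients.

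All four points stand and limit the claim. They do not remove it. The secondary-outcome model is stated and has no term for time observed. The transfusion analysis is open on exactly this question. Continued attendance is encouraged but cannot be assured. A distortion of unknown direction is still a distortion.

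**Conclusion.** The concern holds in a limited form. For hospitalizations and endoscopic interventions, following sections 7.3 and 6.4.2 as written favours whichever arm loses more patients early. For transfusion, the plan specifies neither an analysis nor a treatment of unequal observation time, so the same error is possible but not prescribed.

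At equal true rates with leavers going at month 1, the spurious reduction is about 7% (20% v 10% leaving: 0.867 / 0.933 = 0.93) to 21% (40% v 10%). It is smaller if patients leave later, and absent from the ratio of means if both arms lose patients equally. The loss fractions and leaving times are assumptions, as are the Poisson model and leaving unrelated to bleeding. The direction cannot be stated beforehand. This should be settled before the data are analysed; it does not invalidate the design.

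**What to change.** 1. In section 6.4.2, name the analysis of transfusions, hospitalizations and endoscopic interventions: a Poisson or negative binomial model, chosen in advance, with log(time observed) as offset. Changing the model family without the offset would not help.
2. Report the percentage with zero transfusions as the 3-month Kaplan-Meier estimate of time to first transfusion, censored at last contact.
3. Record the date of each event and of last contact.
4. Extend the continued follow-up in section 7.3 so that these events are ascertained to month 3 for every patient who agrees, including those withdrawn under section 6.3.6. The two sections should be reconciled on this.
5. Add one sensitivity analysis that counts investigator-withdrawn patients in both arms as transfused. An offset or censoring does not correct withdrawal that is related to bleeding.

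The cost is SAP wording, a few date fields and some extra contact with patients who have left. The date fields matter most, because dates are hard to recover later. The downside is that the main analysis assumes censoring unrelated to bleeding; steps 4 and 5 are there to reduce and test that assumption.
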